## 5. Amendments

**Table 1: Amendments**

Amendment number	Reason for amendment	New version number	Effective date
AM01	The global HEM-POWR protocol has been revised to comply with Japanese regulations.	v 1.1_JP	18 MAR 2019

	
The amendment was generated as proof of written-based study design specific in Japan and will be reviewed by the Japanese regulatory authority (PMDA).
 
To avoid redundant description or any conflict, the local Japanese amendment only focuses on critical information for PMDA communication (e.g., number of patients, observation period, timing of interim/final analysis, etc.).
		
--	---	--	--

## 6. Milestones

Table 2 presents planned milestones for the project. These milestones are based on a timely review and approval of the project. Administrative changes to milestones due to delays in study preparation and enrollment do not require amendments to the protocol. Revised study timelines and milestones which do not constitute a need for a formal protocol amendment are kept as a stand-alone document (see Table 6) that is available upon request.

**Table 2: Milestones**

Milestone	Planned date
Start of data collection (First Patient First Visit)	Q2 2019
First interim analysis	1 year after FPFV
Second interim analysis	2 years after FPFV
End of data collection (Last Patient Last Visit)	Q2 2025
Registration in the EU PAS register	Q2 2019
Database clean	Q3 2025
Final statistical analysis	Q4 2025
Final report of study results	Q1 2026

## 7. Rationale and background

### 7.1 Epidemiology, classification, and treatment of hemophilia A

Hemophilia A is an X-linked, inherited, genetic bleeding disorder characterized by deficiency of clotting factor VIII (FVIII) [1],[2]. Hemophilia A comprises approximately 80% of all hemophilia cases, with an annual incidence of approximately 1 in 5,000 live male inhabitants [1],[2]. All races and economic groups are affected equally [1]. Prevalence estimates vary by country, ranging between 5 and 21 cases per 100,000 male inhabitants. According to the World Federation of

Hemophilia, it is estimated that only between 25% and 30% of hemophilia patients globally are adequately diagnosed and managed [3]. Furthermore, up to 75% of hemophilia patients globally live in developing countries in which access to specialist health care professionals and modern therapies prove to be a substantial barrier.

Normal FVIII levels vary between 50% and 150%. The severity of hemophilia A is classified by the amount of clotting factor present in the blood: mild, if the patient has >5% normal clotting factor (>0.05 international units [IU]/mL); moderate, if the patient has between 1% and 5% (>0.01 to 0.05 IU/mL) normal clotting factor; and severe, if the patient has <1% ( $\leq$ 0.01 IU/mL) normal clotting factor. Patients with mild or moderate hemophilia A typically have bleeds only following trauma, and tend to report fewer major health-related quality of life impacts. It is estimated that between 60% and 70% of patients with hemophilia A have the severe form of the disease [4]. For these patients, bleeding events often spontaneously occur in joints or muscles or with minimal or unknown trauma to the affected area [5]. Recurrent bleeding in the joints can lead to progressive joint damage, loss of joint mobility, and chronic pain.

The 2 main approaches to treatment are on-demand therapy, in which the patient is treated in response to a bleed, or prophylactically, in which the patient is treated regularly to prevent bleeding episodes. Prophylaxis is now considered standard of care in many countries, especially in the pediatric and adolescent population, as it has been shown to reduce complications from repeated bleeds, particularly joint arthropathy [2].

## 7.2 Rationale

Damoctocog alfa pegol is a B-domain–deleted recombinant factor VIII (BDD-rFVIII) that is site-specifically conjugated with a 60-kDa branched polyethylene glycol (PEG) molecule at a cysteine that has been introduced into the A3 domain (K1804C) resulting in 1 PEG per BDD-rFVIII protein [6]. This addition of PEG prolongs the duration of FVIII in circulation while retaining its full coagulant activity [7],[8]. Damoctocog alfa pegol is intended for prophylaxis and treatment of bleeds in previously treated patients (PTPs) with hemophilia A aged  $\geq$ 12 years, with a weekly dose that allows for the treatment regimen to be tailored to individual patient needs. An enhanced pharmacokinetic (PK) profile enables a potentially decreased dosing frequency compared with unmodified rFVIII. Efficacy and safety of prophylaxis dosing with damoctocog alfa pegol was demonstrated in 2 phase II/III clinical studies in adult, adolescent, and pediatric (<12 years of age) PTPs with severe hemophilia A [9],[10].

The aim of the proposed study is to characterize in a real-world setting the effectiveness and long term safety of damoctocog alfa pegol drug usage. Detailed information will be collected on reported adverse events (AEs) of interest. These include loss of drug efficacy, hypersensitivity, renal impairment, and neurocognitive disorders. The AEs of hypersensitivity and loss of efficacy are related to the class of FVIII replacement therapy. Since damoctocog alfa pegol is a PEGylated product, immunogenicity related to the PEG component can occur. The 60 kDa PEG that is part of the damoctocog alfa pegol molecule is larger than the 20-40 kDa PEG moieties on other FVIII replacement products. The low content of PEG associated with the site-specific PEGylation of damoctocog alfa pegol results in a lower accumulation of PEG in plasma and tissues relative to some other PEGylated products. The pre-clinical toxicology studies demonstrated an absence of any pathological effects. The low peak plasma level of approximately 0.1 mg/L at steady state in humans is consistent with these pre-clinical data.

These results can be used to educate patients, payors and providers about real-world prophylaxis dosing regimens with damoctocog alfa pegol.

Patients participating in HEMPOWR will be offered to enroll into a sub-study arm evaluating activity with an activity tracking device (ActiGraph; patient will be blinded to the activity tracking device values). The objective of the sub-study is to investigate relationship between patient daily regular activity and efficacy parameters collected from HEM-POWR.

Enrollment into HEM-POWR is not influenced by the patient's decision whether to participate in the sub-study or not. Participation in the sub-study is fully voluntary and will not impact the main objectives or data collected in HEM-POWR. Details of the sub-study, including the analysis of the activity data will be described in a separate sub-study protocol as a part of the main study.

### **7.3 Background**

Prophylaxis with FVIII reduces bleeds and improves joint outcomes in patients with severe hemophilia A [11],[12],[13],[14], and it is therefore the standard of care in most developed countries [2],[15]. However, adherence to prophylaxis is poor in some patients [16]. This may be due to the high time burden and inconvenience of a typical prophylaxis regimen, which requires intravenous infusion at least 2 or 3 times per week [17],[18],[19]. Thus, prolonged-half-life FVIII products that allow for less frequent, individualized dosing may increase adherence and ultimately lead to improved clinical outcomes, including prevention of joint disease [20],[21],[22].

In a phase I study of 14 patients, damoctocog alfa pegol had a half-life of ~19 hours versus ~13 hours for sucrose-formulated rFVIII [8]. In the phase II/III PROTECT VIII study [9], median annualized bleeding rate (ABR) was 2.1 for patients using damoctocog alfa pegol twice weekly, every 5 days, and every 7 days [9], and 1.5 during the long-term extension study. Safety was comparable to that observed with other FVIII products [23],[24],[25],[26],[27]. Patients and physicians can choose from 3 effective prophylaxis regimens with damoctocog alfa pegol based on individual patient bleeding profile and lifestyle. However, there are currently no data regarding real-world use of the product outside of the clinical study.

## **8. Research questions and objectives**

### **8.1 Primary objective**

The primary objective in this study is:

- To assess the effectiveness of prophylaxis with damoctocog alfa pegol in the real-world setting through the collection of total bleeding events and analysis of ABR in the different prophylaxis regimens (following approved local label), or any other regimen prescribed by the physician as part of normal clinical practice) in patients with hemophilia A.

### **8.2 Secondary objectives**

The secondary objectives in this study are to:

- Assess the long term safety of prophylaxis with damoctocog alfa pegol in the real-world setting through the collection and analysis of adverse events (AEs) of special interest (hypersensitivity reactions, loss of drug effect, renal impairment, neurocognitive disorders,

and inhibitor development), AEs, serious adverse events (SAEs), and adverse reactions (ARs).

- Evaluate joint health (Hemophilia Joint Health Score [HJHS]).
- Collect information on affected joints at baseline and in the study.
- Assess hemostasis during surgeries during the study.
- Collect and evaluate patient-reported outcomes such as Hemophilia Treatment Satisfaction Questionnaire for adults (Hemo-SAT A), Hemophilia Quality of Life Measure for adults (Hemo-QoL-A), Hemophilia Quality of Life short form for children (Hemo-QoL-SF) and Work Productivity and Activity Impairment Scale (WPAI [+ CIQ: HS]).

## 9. Research methods

### 9.1 Study design

This is a multinational, open-label, prospective, non-interventional, multicenter, cohort study of PTPs with hemophilia A receiving damoctocog alfa pegol with any kind of treatment modality (on-demand, prophylaxis, or intermittent prophylaxis). The study is planned to be conducted in multiple countries depending on timing of regulatory approval and national reimbursement access.

Prospective data will include prophylaxis regimen effectiveness measured by the number of ABR (reported in patient infusion diaries or documented by physicians, if patient infusion diary is not available), drug usage (IU/kg/infusion, IU/kg/year, and IU/kg/event), regimens used, patient-reported outcome (PRO) measurements (where applicable), such as validated, disease-specific and generic quality of life questionnaires and treatment satisfaction; as well as PK parameters (when available), joint outcomes (HJHS), and safety including AEs of special interest (hypersensitivity reactions, loss of drug effect, renal impairment, neurocognitive disorders, and inhibitor development) and drug-related ARs in standard clinical practice. Retrospective data will include documentation of previous therapy, lifetime duration on prophylaxis, medical condition, PK parameters (when available), and bleeds up to 12 months prior to use of damoctocog alfa pegol, in order to allow a stratification of patients by patient bleeding profile and disease characteristics (See Section 9.3.7).

Patients/legal representatives and physicians can choose from different prophylaxis regimens with damoctocog alfa pegol following approved local labels or any other regimen prescribed by the physician as part of normal clinical practice. Patients/legal representatives and physicians can choose to change the dosing regimen based on the patient's response to treatment at any time. A reason for the dose and/or frequency change should be documented.

The patients planned observation period will be 36 months (with the potential for further extension), for the collection of long-term safety data and continuous prospective monitoring of joint health status over time.

Due to the observational nature of the study no specific follow-up visits can be scheduled and it is unknown when a patient will come for the next visit. Thus data collection occurs continuously throughout the 3 year observational period, i.e. each visit or assessment is to be documented in the eCRF/EDC system. Final data collection should be no sooner than 36 months after the initial visit.

For that reason the data documentation period will continue up to 3 months post Month 36 for the final follow-up time point.

Allocation of a visit or assessment to a specific follow-up time point (e.g. Month 12, 24 and 36, after initial visit) will be done during statistical analysis and will further be described in the Statistical Analysis Plan (SAP).

Interim analyses will be conducted yearly, starting 1 year after FPFV. Interim analyses include analysis of baseline characteristics, prospective treatment outcomes to produce annual safety reports and to provide preliminary results for publications.

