### **9.1.1 Primary endpoint**

The primary endpoint is:

- Mean/median annualized number of reported total bleeds in patients with hemophilia A,

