**Table 3: Tabulated overview on data collected during the study**

	Enrollment/ Initial visit	Follow up visit (including end of observation)
Eligibility Assessment (see 9.2.2)	X	
Date	X	X
Demographic data (see 9.3.3)	X	
General medical/surgical history (see 9.3.5)	X	
Disease history (see 9.3.4)	X	
Bleed history (see 9.3.1)	X	
Prior FVIII treatment history (see 9.3.4)	X	
Damoctocog alfa pegol history (if any, see 9.3.7)	X	
Current prescribed damoctocog alfa pegol regimen (see 9.3.7)	X	X
Damoctocog alfa pegol dose/regimen changes, treatment switches (see 9.3.7)		X (Continuous collection)
Patient-Reported Data (Hemo-SAT A, Hemo-QoL-A, Hemo-QoL Short Form, WPAI [+ CIQ: HS]; see 9.3.10)	X	X (Month 12, 24, 36)

	Enrollment/ Initial visit	Follow up visit (including end of observation)
Physical examination (weight, height, vital signs) 	X	X
Joint Health (HJHS)	X	X
Ultrasound data 	X	X
Affected joints	X	X
Damoctocog alfa pegol Pharmacokinetic analysis  (see 9.3.7)	X	X
Concomitant medication (see 9.3.6)	X	X
Adverse events (includes systematically collected AEs and AEs of special interest (see 11)) 	X (Continuous collection)	
Inhibitor 	X	X
Patient infusion diary		X (Continuous collection)
Physician recorded bleeds 		X (Continuous collection)
Physician recorded surgeries		X (Continuous collection)
Reason for end of observation (see 9.3.11)		X (once, at occurrence)

 Routine examinations only, if available.

 PK analysis is at physician's discretion. PK testing (and the frequency of testing per the table) is part of the routine use of the product.

 Adverse events (up to 30 days after the last treatment with damoctocog alfa pegol in study period).

 Serious, life-threatening bleeds and surgery bleeds to be recorded by the physician. Physician to ask patient at each visit regarding bleeds.

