### 9.3.2 Variables to determine the secondary endpoints

The variables for secondary endpoints are:

- Safety:
  - Occurrence, duration, treatment, severity, and outcome of AEs, SAEs, and ARs (including AEs of special interest [hypersensitivity reactions, loss of drug effect, renal impairment, neurocognitive disorders, and inhibitor development]).
- Effectiveness:
  - Number of reported total, spontaneous, joint, and trauma bleeds.
  - Retrospective (diagnosed clinically, by imaging, by the patient, or by the physician) and prospective location and number of affected joints.
  - Joint health measured by HJHS.
  - Newly affected joints (number and location).
  - Reported bleeds (number, type, location) during study and up to 12 months prior to start of therapy with damoctocog alfa pegol. Prior bleeds to be estimated by the patient and the physician. Reported bleeds during the study will be recorded in the patient infusion diary and serious, life-threatening bleeds and surgery bleeds will be documented by the physician.
  - Number of infusions and FVIII consumption to achieve hemostasis during surgery.
  - Patient-report outcome:
    - Treatment satisfaction measured by Hemo-SAT A.
    - Health-related quality of life measure by Hemo-QoL (A and SF).
    - Work productivity and activity impairment measured by WPAI [+ CIQ: HS].

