### **Analysis populations:**

Patients who took at least 1 dose of damoctocog alfa pegol in the study will be eligible for safety analysis. The full analysis set (FAS) will include all SAF patients who have data on infusions and or bleeding events available. This will include patients who were not followed-up for 3 complete years of prophylaxis. PK analyses will be performed on the PK analysis set. The PK analysis set includes all SAF patients who have evaluable PK data.

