**Factor consumption:**

Factor consumption will be analyzed descriptively based on the patient infusion diary, including the annualized number of infusions per patient, annualized total/average dose, and other infusion characteristics. Summary statistics and frequency tables will be provided per treatment pattern, treated bleeds, and other events (e.g., surgeries).

Sensitivity analyses will be performed in case of incomplete patient infusion diary.

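### Where there is no patient diary, the primary total ABR falls back on physician records, but the only bleeds the protocol tells physicians to record are serious, life-threatening and surgical ones

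*Protocol*

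**What the plan says.** The primary endpoint (Protocol 9.1.1) is "Mean/median annualized number of reported total bleeds in patients with hemophilia A". Section 9.1 gives two sources for it: bleeds are "reported in patient infusion diaries or documented by physicians, if patient infusion diary is not available".

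What the physician records is stated twice. Table 3, footnote 4: "Serious, life-threatening bleeds and surgery bleeds to be recorded by the physician". Section 9.3.2: "serious, life-threatening bleeds and surgery bleeds will be documented by the physician". The same footnote continues: "Physician to ask patient at each visit regarding bleeds". The complete record of bleeding events, with date, location and treatment, is assigned to the diary in 9.3.7, and 9.6 likewise places patient-reported bleeds there.

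Section 9.7.4 estimates mean ABR with a negative binomial model and uses the observed prophylactic treatment period as offset. Under 9.7.1 clinical outcomes are in general not imputed, and the full analysis set (FAS) takes in "all SAF patients who have data on infusions and or bleeding events available". Section 9.9 accepts that for some patients the information may exist only in the physician's documents.

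**The concern.** The protocol makes physician documentation the substitute for the diary without making the two sources equivalent. The diary captures every bleed. The physician is told to record three classes and to ask about the rest, but not to enter the answers. A site that follows the text literally will enter a subset of bleeds for a patient without a diary, and that patient's full prophylaxis time still goes into the offset.

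Three results are exposed. The primary ABR is pulled down. The bleed-free proportion in 9.7.4 is pushed up, because a patient whose bleeds were all non-serious counts as bleed-free. In the comparison with the period before treatment, prior bleeds of all types (estimated by patient and physician under 9.3.2) are set against restricted on-study counts, which favours the product.

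This is a data-collection rule. An analysis plan cannot recover bleeds that were never entered, and the over-dispersion correction deals with variance, not with a shifted mean.

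**Working it through.** **Inputs from Protocol 9.5 and Table 4.** Planning mean ABR μ = 6, dispersion θ = 1, n = 180 evaluable, stated half width 0.96. The ABR of the earlier trial was 4.

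**Inputs the protocol does not give, so assumed.** w = share of patients without a diary (10% to 30% below). r = share of their bleeds that the physician enters (10% to 100%). Patients with and without a diary are taken to have the same true rate and follow-up, and each bleed is taken to be captured independently.

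**Step 1: the plan's own figure.** Half width = 1.96 × √[(μ + μ²/θ)/n] = 1.96 × √[(6 + 36)/180] = 0.947. A simulation with log-scale intervals averages 0.951. Both agree with 0.96 closely enough for it to serve as the yardstick. The probability that 9.5 attaches to this figure is a separate matter and is not used here.

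**Step 2: bias of the pooled mean.** Pooled ABR = (1 − w)μ + w·r·μ = μ[1 − w(1 − r)]. The bias is −μ·w(1 − r), so the relative bias −w(1 − r) does not depend on μ. At μ = 6:

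| w | r = 10% | r = 25% | r = 50% | r = 100% |
|---|---|---|---|---|
| 10% | 5.46 (−9%) | 5.55 (−7.5%) | 5.70 (−5%) | 6.00 (0) |
| 20% | 4.92 (−18%) | 5.10 (−15%) | 5.40 (−10%) | 6.00 (0) |
| 30% | 4.38 (−27%) | 4.65 (−22.5%) | 5.10 (−15%) | 6.00 (0) |

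**Step 3: when the bias equals the planned half width.** Set 6·w(1 − r) = 0.96, so w = 0.16/(1 − r).
- r = 10%: w = 0.16/0.90 = 17.8%
- r = 25%: w = 0.16/0.75 = 21.3%
- r = 50%: w = 0.16/0.50 = 32%
- r = 100%: no bias at any w

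At μ = 4 the same half-width formula gives 1.96 × √(20/180) = 0.653. The crossing points are 0.653/(4 × 0.90) = 18.1% and 0.653/(4 × 0.50) = 32.7%, so the choice of planning mean hardly matters.

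**Step 4: bleed-free proportion, one year, μ = 6, θ = 1.** P(no recorded bleed) = 1/(1 + 6r).
- Full capture: 1/7 = 14.3%
- r = 50%: 1/4 = 25.0%
- r = 10%: 1/1.6 = 62.5%

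Pooled at the crossing points of step 3:
- w = 17.8%, r = 10%: 0.822 × 14.3% + 0.178 × 62.5% = 22.9%
- w = 32%, r = 50%: 0.68 × 14.3% + 0.32 × 25.0% = 17.7%

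**Step 5: before/after comparison.** If the true rate does not change and prior bleeds are fully counted, the recorded on-study to prior ratio is 1 − w(1 − r). At either crossing point w(1 − r) = 0.16, so an apparent 16% reduction arises with no real change.

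**The case against.** The best defence is that the word 'only' is not in the protocol. The sentence in 9.3.2 presupposes a diary and can be read as the usual division of work, with 9.1 as the specific rule when there is none. Footnote 4 has the physician ask about bleeds at each visit, and 11.3 says that bleeds not reported as adverse events are captured in the effectiveness assessment, with no limit to serious ones. This stands in part: it is not established that physicians will omit the other bleeds. But asking is not recording, and the two passages that list what is recorded give the restricted set. At best the fallback is undefined and sites will differ.

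It is also fair that a missing diary should not be presumed common or capture presumed poor. Section 9.9 says only that information may be limited to physician documents, and that patients may keep diaries of their own. The Japanese local amendment (Annex 6: 60 patients, study diary row removed) has physicians refer to the diary used routinely at the site. The physician route is therefore not marginal, but the values of w and r remain assumptions.

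Two stronger readings are tempting and are not supported. A reader might infer that FAS entry depends on having bleed data, so that patients without a diary are selected on the outcome. The rule admits patients with infusion data, bleeding data or both, and 9.3.7 has the physician collect infusion numbers, so a bleed-free patient without a diary can still enter. Exclusion arises only if there is no infusion data and an absence of recorded bleeds is read as an absence of data, which the text leaves open. A reader might also object that the incomplete-diary sensitivity analysis appears only under factor consumption (9.7.5). Section 9.7.4 defers further ABR detail to the SAP, so that is no defect of the protocol.

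**Conclusion.** The inconsistency between 9.1 on one side and 9.3.2 and Table 3 footnote 4 on the other is real and affects how the primary endpoint is collected. Under the literal rule, incomplete capture can only lower the ABR, raise the bleed-free proportion and flatter the before/after comparison.

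The size is illustrative. At a true ABR of 6 the bias matches the planned half width of 0.96 at about 18% without a diary and 10% capture, or about 32% and 50% capture. It is smaller with fewer such patients or better capture, and zero if every bleed is entered. These figures also assume similar true rates with and without a diary. The point warrants a change because the loss happens at data entry and cannot be repaired at analysis.

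**What to change.** 1. Reconcile 9.1, 9.3.2 and footnote 4 of Table 3: where no diary is available, the physician records every bleed since the last visit with date, type and location, or enters an explicit 'none'.
2. Add an eCRF field for the source of the bleed data (diary or physician), so that ABR can be shown by source.
3. As a secondary clarification, word the FAS rule in 9.7.1 so that a documented 'no bleeds' counts as bleeding data. Patients without a diary and without bleeds are then clearly kept.

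Nothing here calls for restricting the primary ABR to part of the patients or person-time.

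The cost is a few sentences, one source field and slightly more eCRF entry for patients without a diary. The question is already asked at each visit, so no visit or procedure is added.
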